7.7 Demographic and Other Baseline Characteristics

Descriptive statistics will be used to summarize demographic and baseline characteristic variables for FAS, MFAS and PRDPS. This will include mean, standard deviation, median, minimum, and maximum for continuous variables, and counts and percentages for categorical variables. Demographic and Baseline variables will be collected through: Medical history coded using the MedDRA dictionary version 20.0 (including surgical, apnea, substance use, and medical therapy such as oxygen use and opioid use), Demographic information, Vital signs, Supplemental oxygen use, Physical exam, Surgery information (post-surgical subjects only) and Medication. The following tables will be reported according to the mock tables presented in the Statistical Programming Requirements document:

Table 8 - Subject Demographics – FAS, MFAS, PRDPS

Table 9 - Subject Physical and Clinical Assessment – FAS, MFAS, PRDPS

Table 10 - Vital Signs/ Resting Baseline per Standard of Care FAS, MFAS, PRDPS

Table 11 - Medical Therapy/Treatments - FAS, MFAS, PRDPS

Table 12 - Surgical Information (for post-surgical patient only) - FAS, MFAS, PRDPS

Table 13 - Medical History Abnormalities by Primary System Organ Class and Preferred Term - FAS, MFAS, PRDPS

Table 14 - Medical History - FAS, MFAS, PRDPS (for a subset of terms if needed)

Table 15 - Surgical History - FAS, MFAS, PRDPS

Table 16 - Apnea History - FAS, MFAS, PRDPS

Table 17 - Substance Use/Smoking History - FAS, MFAS, PRDPS

Table 18 - Medical Therapy History - FAS, MFAS, PRDPS

Medication will be coded using the WHO Drug Dictionary, Version 2009MAR and with the following summary tables:

Table 19 – Medication by WHO Drug Dictionary - FAS

Table 20 – Medication by MedDRA dictionary - FAS

7.8 Treatment Characteristics

Extent of exposure in the population is characterized according to the duration of opioid therapy with monitoring.

Duration of **Opioid Exposure before Monitoring** will be measured in minutes from the start of the Opioid therapy and the starting of the Monitoring: Duration of Opioid Exposure before Monitoring exposure (minutes) = (Start monitoring date/time – Start Opioid therapy date/time). The extent of Opioid Exposure before Monitoring will be presented in a summary table and supporting data listing.

Table 21 – Opioid Exposure before monitoring - FAS, MFAS, PRDPS

Duration of **Monitoring Exposure** will be measured in minutes from the start of the monitoring through and including the time of monitoring end: Duration of monitoring exposure (minutes) = (End monitoring date/time – Start monitoring date/time). Extent of Monitoring exposure will be presented in a summary table and supporting data listing.

Table 22 – Monitoring Exposure - FAS, MFAS, PRDPS

The monitoring exposure will be also described in terms of the quality check, reporting EtCO2 and SpO2 gap overall and during the first 8 hours.

Duration of **Study Exposure** will be measured in days starting from the point of enrollment (informed consent completed and inclusion/exclusion criteria confirmed per the screening evaluation) through and including the time of study exit: Duration of study exposure (days) = (Study Exit date – date of enrollment). Extent of study exposure will be presented in a summary table and supporting data listing.

Table 23 - Study Exposure - FAS, MFAS, PRDPS

Descriptive statistics will be used to summarize study device information for FAS:

Table 24 - Study Device Information - FAS

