9.6. Capnography Monitoring Period

Each subject will be clinically monitored through standard methods (as per clinical practice of the site). Additional continuous data from the Capnostream monitor will be collected for a maximum of 48 hours to identify potential indicators of respiratory depression.

Monitoring of capnography and pulse oximeter data with the Capnostream monitor will start after opioid therapy has been initiated for subjects that will receive their first opioid therapy dose while on the hospital ward. The monitoring period will start for subjects once they arrive on the ward, for those subjects where opioid therapy was initiated prior to arrival on the hospital ward.

Monitoring may be discontinued after a minimum of 4 hours from the last dose of opioid therapy received or if the subject is discharged from the hospital ward.

Monitoring duration may be determined in periods, as deemed clinically appropriate during opioid therapy. An example of monitoring split into three periods:

PRODIGY CIP

- Period 1: first 24 hours continuous monitoring after enrollment (mandatory).
- Period 2: 12 hours continuous monitoring (to be performed for guidance during the first night following Period 1, from 7pm to 7 am).
- Period 3: 12 hours continuous monitoring (to be performed for guidance during the second night following Period 1, from 7pm to 7 am).

The suggested monitoring setting for Periods 2 and 3 has been proposed to facilitate subject's motion during daytime, thus covering the nighttime period at higher risk of developing RD events⁶. The alarm feature of the monitoring device will be silenced and the screen information blinded. A periodic check during the monitoring period should be completed to ensure the etCO₂ filter line and SpO₂ sensor are appropriately fitted on the subject.

Apart from the capnographic monitoring, no other device or concomitant medications different from clinical practice may be used during PRODIGY Study.

The Monitoring eCRF will be completed to document:

- Care pathway (location/transfers within the hospital)
- Monitoring duration
- Vital signs
- Supplemental oxygen use
- Medications
- Product information

At the end of the monitoring period the subject will be treated according to the hospital clinical practice and remain in the study for a maximum period of 30 days from the start of opioid therapy.

9.7. 1-Month Follow Up

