7.6 Derived variables

The statistical evaluations will use some derived variables as listed below. All additional derived variables or changes on the variable listed below are reported in the Statistical Programming Requirements document.

New Variables	Derivation
Monitoring Exposure (minutes)	End monitoring date/time – Start monitoring date/time
Study Exposure (days)	(Study Exit date – date of enrollment)/30.44
BMI35	If BMI >35 then BMI35=1 otherwise BMI35=0
Obese	If BMI >30 then Obese=1 otherwise Obese=0
AGE50	If Age >50 then AGE50=1 otherwise AGE50=0
AGE65	If Age >65 then AGE65=1 otherwise AGE65=0
STOP BANG SCORE	The score is the sum of the following points for each patient: If Snoring loudly= Yes then add 1 point If Tiredness in daytime= Yes then add 1 point If Observed apnea during sleep= Yes then add 1 point If Treated for High blood Pressure= Yes then add 1 point If Body mass index >35 (kg/m2) then add 1 point If Age >50 years then add 1 point If Neck circumference >40 cm (16 inches/17inches according to gender) then add If Gender = Male then add 1 point
Opioids Tolerant §	The FDA definition will be used: A patient is considered opioid tolerant if for at least 1 week he/she has been receiving one of the following: 
 • 60 mg oral morphine/day • 25 mcg transdermal fentanyl/hour • 30 mg oral oxycodone/day • 60 mg oral hydrocodone/day • 8 mg oral hydromorphone/day • 25 mg oral oxymorphone/day • Equi-analgesic dose of any other opioid The Morphine Milligrams Equivalent will be used.
STOP BANG SCORE Class	If 0≤STOP-BANG score ≤2 then STOP BANG SCORE Class= 1 labeled as “Low risk of OSA” If 3≤STOP-BANG score ≤4 then STOP BANG SCORE Class= 2 labeled as “Intermediate risk of OSA” If 5≤STOP-BANG score ≤8 then STOP BANG SCORE Class= 3 labeled as “High risk of OSA”
High Risk Surgery	If occurred within 24 hours
Known or suspected sleep-disordered breathing§	if “Yes to OSA (from Medical History) + YES to first 4 questions of the Apnea History
PCA or epidural or intrathecal therapy	PCA with route as epidural or intrathecal from CM
Multiple opioid or concurrent CNS/sedating medication	According to the Medication coding *(benzodiazepines, sleep aids, muscle relaxant, etc.)
Opioid dosage	According to the Medication coding * (>30mg oral morphine per day or equivalent)
Major organ failure	According to the coding °
Diabetes	if “Yes to Diabetes type I or II”

New Variables§	Derivation

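### SAP Monitoring Exposure is a single end-minus-start difference, which on its natural reading counts off-device hours as monitored for subjects observed in separate periods

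*SAP*

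**What the plan says.** SAP 7.8 describes Monitoring Exposure as time that "will be measured in minutes from the start of the monitoring through and including the time of monitoring end", and then gives the formula: "Duration of monitoring exposure (minutes) = (End monitoring date/time – Start monitoring date/time", closing the bracket there. SAP 7.6 has the same derivation, "End monitoring date/time – Start monitoring date/time". Both are worded for one start and one end. The result goes to Table 22 (FAS, MFAS and PRDPS) and a supporting listing. SAP 7.8 adds that EtCO2 and SpO2 gaps will be described as a quality check, overall and for the first 8 hours.

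Protocol 9.6 sets the limit: "Additional continuous data from the Capnostream monitor will be collected for a maximum of 48 hours". It also says "Monitoring duration may be determined in periods, as deemed clinically appropriate during opioid therapy" and offers "An example of monitoring split into three periods":

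- The first is "Period 1: first 24 hours continuous monitoring after enrollment (mandatory", the only one marked as required.
- The second is 12 hours overnight, 19:00 to 07:00, on the first night after Period 1.
- The third is "Period 3: 12 hours continuous monitoring (to be performed for guidance during the second night following Period 1, from 7pm to 7 am".

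The stated purpose of this layout is to leave subjects free to move about in the daytime. SAP 7.1.3 keeps subjects whose monitoring was intermittent or stopped early in the MFAS.

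**The concern.** The formula is correct only for uninterrupted monitoring, yet both documents foresee interruption. Under the example schedule the device is off by design for at least one full daytime, and a single difference between end and start includes those hours. A subject who followed the example exactly would then be reported with more monitoring than the protocol permits.

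This matters because RD is identified mainly from device memory data, so time on the device is the window in which most RD can be detected. Table 22 is where a reader learns how long that window was. The SAP also already separates monitored from unmonitored time elsewhere: SAP 7.10.2.2 leaves clinical events outside monitoring out of its accuracy tables. An event in a daytime gap would be treated there as unmonitored, while the same hours counted as monitored in Table 22.

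**Working it through.** **Inputs.** Period lengths of 24, 12 and 12 h, night clock times of 19:00 to 07:00, and the 48 h maximum come from Protocol 9.6. The formula comes from SAP 7.6 and 7.8. The documents give no clock time for the start of Period 1, so it is varied here. Call it s, in hours after midnight.

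**Step 1: reproduce the plan's figure.** Monitored time = 24 + 12 + 12 = 48 h (2,880 min), which equals the protocol maximum.

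**Step 2: elapsed span.** Let g be the gap from the end of Period 1 to the next 19:00. The gap between Periods 2 and 3 runs from 07:00 to 19:00, which is 12 h. Then

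span = 24 + g + 12 + 12 + 12 = 60 + g, and off-device time = 12 + g.

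**Step 3: daytime starts (07:00 to 19:00).** Period 1 lasts 24 h, so it ends at clock time s. Hence g = 19 − s and span = 79 − s.

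| Period 1 start | Span (h) | Monitored (h) | Off-device (h) | Span / monitored |
|---|---|---|---|---|
| 07:00 | 72 | 48 | 24 | 1.50 |
| 10:00 | 69 | 48 | 21 | 1.44 |
| 12:00 | 67 | 48 | 19 | 1.40 |
| 15:00 | 64 | 48 | 16 | 1.33 |
| 19:00 | 60 | 48 | 12 | 1.25 |

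In minutes this is 3,600 to 4,320 against 2,880.

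**Step 4: overnight starts (after 19:00, before 07:00).** The protocol does not say what happens when Period 1 ends during a night, so two readings are shown.

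- *Two full later nights are required.* This keeps the stated 12 h lengths. Here g lies between 12 and 24 h, so the span is just over 72 to just under 84 h for 48 h monitored. A 20:00 start gives 83 h; a 02:00 start gives 77 h.
- *Period 2 is the rest of the night in progress.* Monitored time falls to about 36 to 48 h and the span is about 48 to 60 h. A 20:00 start gives 59 h for 47 h monitored; a 02:00 start gives 53 h for 41 h. Exactly 12 h off the device is counted.

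**Step 5: who is affected.** Anyone who completes all three periods has at least 12 h of off-device time counted. A subject with a daytime start who stops after Period 2 has 36 + g against 36 h, an excess of 0 to 12 h. A subject monitored in one continuous 48 h run is reported correctly as 48 h.

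**The case against.** The strongest reply is that the SAP is under-specified on this point, not demonstrably wrong. It never says first start or last end. If the monitoring records hold one start and one end per period, the same formula applied to each record and summed gives 48 h. SAP 7.6 also refers changes in listed variables to the Statistical Programming Requirements document, which is not available here and may settle the matter. The three-period layout is an example given for guidance, monitoring may end sooner, and nothing shows how many subjects would be monitored in periods. The gap report in SAP 7.8 might reveal the off-device hours.

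Much of this stands. The first-start-to-last-end reading is inferred from singular wording. The percentages describe a subject who completes the example, not the expected shift in a Table 22 mean or median. But the formula appears twice with no mention of summing, and a possible correction in another document does not repair it. The SAP does not say that gaps are subtracted from exposure, or that planned off-monitor intervals count as gaps.

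A reader might also infer damage further on: wrong RD rates per monitored hour, subjects wrongly passing a minimum-monitoring check, or distorted comparisons between sites. The documents do not support these:

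- The primary model (SAP 7.10.1.1) is logistic, with one row per patient, a yes/no outcome and baseline predictors. It has no exposure term.
- Protocol 13.4 plans event-rate models but names no denominator.
- SAP 7.1.3 retains subjects with short monitoring and uses their data, so no exclusion depends on this variable.
- Table 22 is laid out by analysis set, not by site.

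**Conclusion.** The definition does not fit subjects monitored in separate periods and should be corrected. For completers of the example schedule, its natural reading overstates monitored time by 12 to 24 h (+25% to +50%) with a Period 1 start between 07:00 and 19:00. With an overnight start and two full later nights, the overstatement is just over 24 to just under 36 h (more than +50%, less than +75%). These figures assume one start and one end per subject, adherence to the example's clock times, and no correction in the programming document. The effect on the Table 22 summary cannot be sized, because the proportion monitored in periods is not given. The established consequence is confined to Table 22 and its listing; the risk score and the stated endpoint analyses are not shown to be affected.

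**What to change.** In SAP 7.6 and 7.8, define Monitoring Exposure as the sum over monitoring periods of (period end − period start), taken from the monitoring records or the device memory time stamps, and use that figure in Table 22 and its listing. If the elapsed time from first start to last end is also wanted, report it under a separate name. State whether planned off-monitor intervals count as gaps in the EtCO2/SpO2 description. Carry the same definition into the Statistical Programming Requirements document.

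The cost is a few lines of SAP text and a small programming change; the protocol already collects monitoring duration and device memory data. Reported exposure will be smaller for intermittently monitored subjects and unchanged for those monitored in one run.

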7.9 Interim Analyses

Interim analyses are not planned for this study.

7.10 Evaluation of Objectives

In this section a detailed information about each objective is included together with calculations and derivations of outcome parameters (see table in section 7.6), analysis methods, datasets analyzed (FAS, MFAS or PRDPS) and additional analyses where applicable.

7.10.1 Primary endpoint

The primary endpoint that will be used to derive and validate the risk score assessment is the RD episode, defined as a clinical diagnosis made after reviewing monitoring data in conjunction with the clinical data and consistent with accepted pathophysiologic mechanisms. The primary endpoint used to derive the score will be the occurrence of RD episodes captured by continuous capnography and pulse oximetry measurements recorded on the Capnostream device memory data in conjunction with the clinical data as reported by the Investigators. RD determination will be validated by an independent Clinical Event Committee (CEC). The CEC will use both clinical data and monitor parameters specified below as a guideline; if determination of an RD episode is clinically appropriate but outside of the guidelines a rationale will be provided. Data suggestive of an RD episode include any of the following:

RR ≤ 5 breaths for ≥ 3 minutes
SpO2 ≤ 85% for ≥ 3 minutes

etCO ₂ ≤ 15 or ≥ 60 mmHg for ≥ 3 minutes
Apnea episode lasting > 30 seconds
Any respiratory Opioid-Related Adverse Event (rORADE)

The assessment of RD episodes will be made by the analysis of the Capnostream and clinical data for each patient. For each patient all potential RD episodes will be derived using the Detection Tool (see section 9.3) and will be submitted to the CEC according to a Priority List (see section 9.4) in order to adjudicate the potential RD episodes starting from RD episodes most likely to be RD. The CEC adjudication will stop the adjudication at the first RD occurring per patient (all details on CEC process are reported in the CEC Charter version 3.0).

All potential RD episodes in the study will be always rated by 3 coders (see detail in the Clinical Events Committee Charter Template, Version 3.0).

Patients of the MFAS will be randomly assigned (2:1) into respectively the derivation and the validation cohort. In case of low enrollment rate or low episode rate or according the outcome of a preliminary assessment of the events per variable or unbalanced enrollment per site/country the MFAS could not be randomized but used for model building and the bootstrap method, deriving 500 computer-generated samples by random selection with replacement for model validation³ (see section 9.2 for details).

7.10.1.1 Deriving the model

Note for Programmer: The analysis for the primary objective will be performed on a Dataset with one row per patient with RD episode as validated by CEC as the dependent variable (at least one RD) and baseline predictors as independent variables. Potential predictors will be reported on continuous scale or grouped into categories.

The logistic model will be used for bivariate e multivariate odds ratios (ORs) and 95% confidence intervals (95% CIs) will be estimated for each potential predictor. The following steps will be followed to derive the score for each predictor according to categories⁴:

- Determine categories for each risk factors (the most will be 0/1)
- Determine reference class for each risk factor (for dummy the reference category is 0)
- Calculate mid-values to represent categories
- Determine multiplier β
- Determine point score for each risk factor category

If **Data Split** approach:

- Repeat multivariate model on the validation set
- Calculate performance measures
- The "Optimism" is the difference between the performance measures from validation and derivation set

If **Bootstrapping** approach:

- 500 bootstrapped replications of the multivariate model

- Calculate performance measures bootstrapped
- The difference between the bootstrapped performance and the model performance will be averaged to obtain an estimation of the “optimism” of the model. The optimism will be used to validate the model.

Table 25 - RD Risk Score Derivation identified by logistic – MFAS

Predictors	Bivariate analysis OR (95% CI) (N=XXXX)	Multivariate analysis OR (95% CI) (N=XXXX)	Coefficient	Adjusted Coefficient	Risk score point
Char#1	x.xx (x.xx- x.xx)	x.xx (x.xx- x.xx)	x.xxx	x.xx (x.xx- x.xx)	xx
Char#2	x.xx (x.xx- x.xx)	x.xx (x.xx- x.xx)	x.xxx	x.xx (x.xx- x.xx)	xx
...					
Char#N	x.xx (x.xx- x.xx)	x.xx (x.xx- x.xx)	x.xxx	x.xx (x.xx- x.xx)	xx

The collinearity between categorical variables will be also tested by means the Cramer V test for nominal variables and Kendal’s tau-b for ordinal variables. The multivariate logistic regression model will be performed using a stepwise selection procedure in which the presence of event will be the dependent variable. Independent predictors will be entered in to the model if a significant association, defined as $p \leq 0.05$, will be identified from bivariate analysis and, to avoid over-fitted and unstable model the correlation coefficient between them should be less than 0.25.

The predictive risk score for RD, based on the best model selected from analysis above, will be calculated by multiplying each β coefficient taken from the final multivariate model by 10 and rounding to the nearest integer. The integers will then be added together to produce an overall RD risk score for each patient. The resulting continuous distribution of total risk scores across all patients in the derivation set will be then stratified into categories of points (depending on the total sample the quintiles or tertiles or optimal cutoff points) that grouped patients according to the level of risk.

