6.2. Rationale

The need of a simple tool to stratify patients at risk for developing RD has been identified to understand individuals that may benefit from capnographic monitoring. The chosen study design was based on predictive models that are often used to predict the probability that a subject with a given set of risk factors will experience an outcome. However the predictive ability of the model should be evaluated before any use in clinical practice. This is known as the validation step. The standard regression method used for analysis could accurately predict outcomes for subjects in the dataset used to develop the model, but may often perform less well in a new subject group. This difference is due to the random variation present in the development dataset. Therefore, the need to validate the risk score in another validating set of subjects has been incorporated.

This study will also collect data on a high number of subjects monitored by capnographic monitoring, thus allowing understanding of the real incidence of RD, especially in non-surgical subjects for which there are no data in the literature.

7. Product Description

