5.1 Study design

PRODIGY is a prospective, multi-center, post-market interventional, international cohort study. The study population consists of subjects of adult age (≥ 18 in US and Europe, ≥ 20 in Japan, ≥ 21 in Singapore) receiving parenteral opioid therapy for pain while on the hospital ward.

A derivation cohort will be used to derive the risk assessment tool. An internal validation cohort will be used for evaluating the prognostic value of the score for the prediction of RD. Capnography and pulse oximetry monitoring device data will be collected as well as interventions related to respiratory depression. Subjects will be monitored per standard of care.

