7.10.1.2 Validating model on validation cohort

Model prediction performance will be assessed as for the derivation cohort using calibration (the agreement between predicted and observed outcome) and discrimination (the ability to separate patients with and without the outcome) and the R^2 will be reported as an overall measure for discrimination and calibration. The Sensitivity, Specificity, Positive Predictive Value (PPV), Negative Predictive Value (NPV) and the Receiver Operating Characteristic (ROC) curves will be used to visualize the overall accuracy of the model (see section 9.1 for detail on aspect to be checked for model validity).

Table 26 - Sensitivity, specificity, PPV and NPV of the Risk Score to predict high risk subjects – Validation Cohort - FAS

Accuracy Measure	Optimal Cut-off %(IC)
Sensitivity	X% (Y%-Y%)
Specificity	X% (Y%-Y%)
PPV	X% (Y%-Y%)
NPV	X% (Y%-Y%)
...	...

Figure 3 – Receiver Operating Characteristics curve on Validation Cohort-FAS

Figure 4 – Agreement between observed frequency and predicted probability on Validation Cohort- FAS

The discriminatory performance of the model will be validated by comparing the receiver-operating characteristic (ROC) curve analysis in the derivation set with that in the validation set.

Figure 5 – Comparison between ROC curves on Derivation and Validation Cohorts-FAS

Figure 6 – RD rate according to the Risk Score in Derivation and Validation Cohorts-FAS

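### The SAP's bootstrap optimism compares two in-sample figures and corrects nothing, and its data-split step needs reconciling with the planned held-out assessment of the RD score

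*SAP*

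**What the plan says.** **Bootstrap route.** SAP 7.10.1 allows this route for low enrolment, a low episode rate, the events-per-variable assessment, or imbalance by site or country: "the MFAS could not be randomized but used for model building and the bootstrap method". SAP 7.10.1.1 then says "The difference between the bootstrapped performance and the model performance will be averaged to obtain an estimation of the" optimism of the model. Section 9.2 gives the same rule for R² (mean over 500 replicates against the model's own R²), reruns the univariate and multivariate models in each replicate, and takes the resulting optimism as the validation. It also says that bootstrapping gives unbiased accuracy estimates.

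**Score.** Points come from each coefficient "taken from the final multivariate model by 10 and rounding to the nearest integer". Table 25 has an Adjusted Coefficient column that is not defined anywhere.

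**Data-split route.** SAP 7.10.1.1: "Repeat multivariate model on the validation set", then calculate performance and call the validation–derivation difference optimism. Other text points to one derived score assessed in held-out patients:
- SAP 5.1: "An internal validation cohort will be used for evaluating the prognostic value of the score for the prediction of RD".
- SAP 7.10.1.1: "The resulting continuous distribution of total risk scores across all patients in the derivation set will be then stratified into categories of points".
- SAP 7.10.1.2, Table 26, for the validation cohort: "Sensitivity, specificity, PPV and NPV of the Risk Score to predict high risk subjects".
- Protocol 6.2: "the need to validate the risk score in another validating set of subjects has been incorporated".

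**Slope.** SAP 9.1 gives a target calibration slope of 1 for the predictive score, and its formula names mortality as the outcome.

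**The concern.** The primary objective is to derive and validate the tool. Protocol 6.2 gives the reason for validating: a model can predict well in the data that built it and less well in new subjects. An optimism estimate should measure that loss.

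The bootstrap rule as written sets one in-sample figure against another, and neither shows how a fitted model does on data that it was not fitted to. The result also changes nothing that is reported. This route has no separate validation cohort, so nothing else in the plan makes up for the gap.

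On the split route, a literal refit would again compare two apparent performances. The optimism figure could then disagree with the validation results in 7.10.1.2.

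**Working it through.** **Plan's own figures.** The documents give no value for optimism. The sample size, which sets the scale here, reproduces: 12 variables × 10 events = 120; 120 / 0.12 = 1000 for derivation; 1000 × 1.5 = 1500; 1500 × 1.10 = 1650. The validation set of 500 would have about 500 × 0.12 = 60 subjects with RD.

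**Bootstrap rule.** Let A be the original model's performance on the original sample. Let B be a resample model's performance in its own resample, and T the same model's performance on the original sample.
- SAP: mean(B) − A
- Standard: mean(B − T)
- Standard minus SAP: A − mean(T), the term that the SAP never computes
- True optimism: A minus performance in new patients

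The calibration slope needs no assumed effects. A logistic model fitted by maximum likelihood has log-odds slope 1 in its own data, so B = 1 and A = 1. The SAP difference is 1 − 1 = 0 however overfitted the model is.

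For R², predictor effects must be assumed. One simulation (n = 1500, 12% RD, 12 binary predictors with prevalence 10–40%, moderate effects with log-odds ratios 0–0.6, Nagelkerke R², 80 datasets × 60 resamples) gave:

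| Setting | A | mean(B) | New patients | SAP | Standard | True |
|---|---|---|---|---|---|---|
| Moderate effects, with selection | 0.0703 | 0.0844 | 0.0372 | 0.0141 | 0.0299 | 0.0331 |
| Moderate effects, all 12 fitted | 0.0843 | 0.0991 | 0.0418 | 0.0148 | 0.0317 | 0.0425 |
| No effects, all 12 fitted | 0.0139 | 0.0293 | −0.0162 | 0.0154 | 0.0326 | 0.0301 |

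In the first row the SAP figure is 0.0141 / 0.0331 = 43% of true optimism. The plan would report 0.0703. The standard correction gives 0.0703 − 0.0299 = 0.0404, against 0.0372 in new patients.

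A larger simulation used 12 independent predictors at 30% prevalence, a p ≤ 0.05 screen plus backward selection, and 300 datasets × 100 resamples. SAP / true R² optimism at 12% RD:
- 4 predictors at OR 1.5: 0.013 / 0.021
- 4 at OR 2: 0.012 / 0.017
- 12 at OR 1.3: 0.017 / 0.033
- 12 at OR 1.5: 0.015 / 0.044

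That is 35–69% of true before rounding, and 46–70% at 6% RD. Smaller repeats at 12% RD gave 49% (0.017/0.035) to 76% (0.013/0.017). With weak effects (OR 1.1–1.2) the SAP figure was 94–100% of true at 12% RD and 102–119% at 6%. With null effects it was 127% and 145%. The standard rule gave 81–132% (12% RD) and 85–115% (6% RD) for moderate effects, 139–171% for weak and 183–207% for null.

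Across all 14 settings (seven effect patterns, two RD rates), apparent R² averaged 0.010–0.053 above new-patient R². Subtracting the standard optimism left a smaller average error than subtracting nothing in 13. The exception was null effects at 6% RD (0.014 against 0.013).

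**Split rule.** If the selected variables are refitted on the validation set, the refit's log-odds slope is 1 by construction. Drop in c-statistic from derivation (1000/500, 12% RD, 2000 simulated trials per pattern, those selecting at least one predictor):

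| Assumed effects | Refit | Derivation model held fixed | Median slope, fixed model |
|---|---|---|---|
| 4 at OR 1.5 | 0.023 | 0.041 | 0.62 |
| 4 at OR 2 | 0.003 | 0.022 | 0.88 |
| 12 at OR 1.3 | 0.036 | 0.059 | 0.48 |
| 12 at OR 1.5 | 0.031 | 0.058 | 0.65 |
| 4 at OR 1.2 | 0.030 | 0.054 | 0.21 |
| 12 at OR 1.1 | 0.032 | 0.056 | 0.17 |
| All null | 0.029 | 0.061 | – |

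Here a refit shows between 14% (0.003/0.022) and 61% (0.036/0.059) of the loss. The fraction depends on the setup: with all 12 null predictors fitted, c rose from 0.590 to 0.632 on refitting, while the fixed model fell to 0.494.

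**The case against.** **The split route already has a held-out assessment.** A reader might infer that the plan never tests the score outside its fitting data. The documents do not support that. SAP 7.10.1.2 is a separate validation section with accuracy measures for the risk score, observed against predicted risk, ROC curves compared between cohorts, and RD rate by score. The verb in 7.10.1.1 is ambiguous, and if it means apply, the split step is sound. This objection stands and reduces the split part to a reconciliation. Even so, no passage says that coefficients, points or cut-off are held fixed.

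**Bootstrap is only an option.** Correct: Protocol 13.3 and SAP 7.2 permit it without requiring it. The defect applies if that route is taken.

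**An adjustment may have been intended.** The Adjusted Coefficient column hints at one. It is undefined, and the text builds the points from the final model's own coefficients, so it repairs nothing as written.

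**The SAP difference is not always too small.** A reader might infer that it always understates optimism, or that the standard rule is always better. Neither holds. In the six weak or null settings of the larger simulation the SAP difference was nearer the truth and the standard rule over-corrected. Subtracting even the SAP difference (35–145% of true) would have beaten subtracting nothing in all 14 settings. The simulations therefore support subtracting an optimism estimate more firmly than they rank the two estimators.

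**The absolute inflation is small.** An R² excess of 0.010–0.053 is modest in absolute terms. It is large beside an R² of this size: 0.0703 apparent against 0.0372 in new patients in the first bootstrap row.

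**Conclusion.** The bootstrap procedure is wrong as written and should be fixed. Both SAP descriptions agree, neither tests a replicate model on the original sample, and neither corrects the reported performance. This conclusion rests on the text and on the slope identity, not on simulation.

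The size does rest on assumptions, because the documents give no predictor effects and do not say which R² is meant. With moderate effects and 12% RD the SAP difference is roughly 35–80% of true R² optimism; with weak or null effects it can equal or exceed it. The effects, prevalences, independence of predictors and Nagelkerke R² are all assumed.

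The split step is an inconsistency to reconcile. Its most natural reading is a refit, at odds with the rest of the plan, but the plan does contain a held-out assessment of the score.

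The slope definition in 9.1 is a minor point. A target of 1 fits only the log-odds linear predictor. If the score meant the 10 × β points, good calibration would be about 0.1 per point.

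**What to change.** **SAP 9.2 and the bootstrap bullets of 7.10.1.1.** In each of the 500 resamples, repeat screening, selection and fitting; 9.2 already reruns the univariate and multivariate models. Take optimism as the resample model's performance in the resample minus that same model's performance on the original MFAS. Average it, subtract it from the apparent c-statistic, R² and calibration slope, and report the corrected values. Note that the correction may be conservative if predictors are weak.

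**Table 25.** Define the Adjusted Coefficient column and say whether the points use it, or delete it.

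**Split bullets of 7.10.1.1.** Replace the repeat step with: apply the derivation-set coefficients, points, categories and cut-off unchanged to the validation set. Define optimism as derivation minus validation performance of that fixed score. Say the same in 7.10.1.2 and for the Table 26 cut-off.

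**SAP 9.1.** State that the slope is for RD, not mortality, on the log-odds linear predictor.

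**Cost.** SAP wording and a little code, with no new data. Reported performance will usually be slightly less favourable, and may be over-corrected if predictors are weak.
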